### **3.8.3.2 ORR using Kadmon Algorithmic Response Assessment (KARA)**

In addition to ORR assessed by investigators, the sponsor will conduct response assessments according to criteria listed in Appendix B for each individual organ, then assign overall response according to [Table 2](#) (cGVHD response definitions). Analyses of ORR and DOR will be repeated with this sponsor assessment of overall response.

Concordance with investigator determined responses will be analyzed.

### **3.8.4 Subgroup Analyses**

Subgroup analyses for the endpoints of ORR and DOR will be conducted for the following subgroups:

- Prior ibrutinib (Yes / No)
- Severe cGVHD at screening (Yes / No)
- Number of organs involved at baseline (<4 /  $\geq$ 4)
- Number of prior lines of therapy ( $\leq$ 3 /  $>$ 3)
- Duration of cGVHD before enrollment (by 50th percentile)
- Baseline corticosteroid dose level (by 50th percentile)
- Lung involvement at baseline (Yes / No)
- Take concomitant medication proton pump inhibitor (PPI) on C1D1 (Yes/No)
- Gender
- Age (<65,  $\geq$ 65 years))
- Race
- Prior ruxolitinib (Yes / No)
- Best response to the last prior treatment (SD/PD)
- Take concomitant medication proton pump inhibitor (PPI) on C1D1 (Yes/No)
- Baseline GFR (<60, 60-90 and  $\geq$ 90 mL/min)

All subgroup analyses will be exploratory and with no multiplicity adjustment.

### **3.8.5 Multivariate Modeling**

Logistic regression will be carried out as exploratory/supportive analyses. This will provide a means to assess the effects of those potential prognostic indicators listed in subgroup analyses section. The following modeling procedure will be used:

- **Univariate modeling**

A logistic regression model (response ~ an individual factor) will be used for a factor of arm, potential prognostic factors listed in subgroup analyses section and other potential prognostic indicators. The resulting odds ratio, its confidence interval (CI) and p value will be summarized in a univariate analysis table.

- **Multivariate modeling**

Based on the univariate modeling results and clinical judgement, a multivariate logistic regression model might be chosen as a predictive model.

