## 2.4 Randomization

Subjects will be randomized to either Arm A (200mg QD) or Arm B (200mg BID) with 1:1 ratio and block size 4. Randomization will be stratified according to:

- Prior ibrutinib therapy (Yes / No)
- Severe cGVHD (yes/no) where severe cGVHD is defined as at least one organ with a score of 3, or a lung score of 2 or 3

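### The exploratory QD-versus-BID odds ratio is fitted without the two randomization strata, so its interval and p-value are conservative if those strata predict response

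*SAP*

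**What the plan says.** SAP 2.4 allocates participants "with 1:1 ratio and block size 4", stratified by prior ibrutinib therapy and by severe cGVHD, each yes or no. Protocol 5.3 gives the same two factors and block size.

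SAP 3.8.5 then says: "A logistic regression model (response ~ an individual factor) will be used", first for arm, and applies the same one-factor form to the factors on the subgroup list. Each model yields an odds ratio, a confidence interval and a p-value. Both stratification factors are on that list (SAP 3.8.4), which 3.8.5 describes as potential prognostic indicators. Each therefore gets its own model, but neither is in the model for arm.

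The section labels its own status: "Logistic regression will be carried out as exploratory/supportive analyses". Its second step is that, depending on the univariate results and clinical judgement, "a multivariate logistic regression model might be chosen as a predictive model". That step is optional, and no covariates are fixed for it, neither arm nor the strata.

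The primary analysis is separate. Each arm's ORR is set against 30% with exact intervals and the Hochberg procedure (SAP 3.1, 3.2 and 3.8.1), and alpha goes only to that endpoint (SAP 3).

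**The concern.** When a trial stratifies its randomization, the usual analysis conditions on the strata. Permuted blocks within strata make the arms more alike on prior ibrutinib and severity than simple randomization would, so the arm estimate varies less from trial to trial. A model with arm alone computes its standard error as if that balance were absent. If the strata predict response, the stated standard error is too large for the quantity being estimated: the interval is too wide and the p-value too high.

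The odds ratio also changes meaning when prognostic covariates are left out. The one-factor model estimates a marginal odds ratio, and the stratified model estimates the odds ratio within strata, which lies further from 1 when the arms differ.

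Secondary endpoints are descriptive, and I find no other planned between-arm estimate of response with an interval and p-value. The one formal estimate of the randomized dose contrast is therefore the one that does not reflect how participants were randomized. If an adjusted model is fitted later under the optional step, its covariates will have been chosen after seeing the univariate results.

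**Working it through.** **The plan's own figure.** The documents give no figure for the arm odds ratio or its precision. The one design figure, 63 per arm, reproduces. Counting dropouts as non-responders, the rate is 0.55 × 0.9 = 0.495. By normal approximation n = [(2.005 × √(0.3 × 0.7) + 1.282 × √(0.495 × 0.505)) / 0.195]² ≈ 64. Exactly, 27 or more responses of 63 give one-sided alpha 0.0206 and power 88.1%.

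**Inputs.** From the documents: 63 per arm, 1:1, blocks of 4 within strata. Assumed, because the documents give no values: 30% prior ibrutinib (protocol 4.1 gives only a target of at least 10%), 65% severe cGVHD, response odds of 3 in the reference arm when neither factor is present, and the same odds ratio for each stratum factor, varied over 0.25, 0.4 and 0.6.

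**Marginal against conditional odds ratio** (stratum OR 0.25, conditional arm OR 2.0).
- Stratum weights: neither factor 0.7 × 0.35 = 0.245; ibrutinib only 0.105; severe only 0.455; both 0.195.
- Reference arm: odds 3, 0.75, 0.75 and 0.1875, so rates 0.750, 0.429, 0.429 and 0.158; weighted mean 0.4545.
- Other arm: odds doubled, so rates 0.857, 0.600, 0.600 and 0.273; weighted mean 0.5992.
- Marginal OR = (0.5992/0.4008) / (0.4545/0.5455) = 1.79.
- With stratum OR 0.4 the same steps give 1.90.

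**Standard error of the log odds ratio.**
- One-factor, stratum OR 0.25: √[1/(63 × 0.4545 × 0.5455) + 1/(63 × 0.5992 × 0.4008)] = 0.361.
- With both strata in the model (Fisher information): 0.395.
- At stratum OR 0.4: 0.374 and 0.390.
- Adjustment raises the standard error. It still gains power, because the estimate moves further: ln(1.79)/0.361 = 1.61 against ln(2.0)/0.395 = 1.75.

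**Calibration when the arms are equal** (stratum OR 0.25, 3,000 simulated trials, N = 126, stratified blocks of 4).
- One-factor model: mean stated SE 0.361, actual SD of the estimate 0.331. A nominal 5% test should then reject 2 × [1 − Φ(1.96 × 0.361/0.331)] = 2 × [1 − Φ(2.14)] ≈ 3.2%. The simulation gave 3.0%.
- Adjusted model: mean stated SE 0.398, rejection 4.9%.
- A repeat set of 3,000 trials gave 3.2% and 5.4%, with adjusted SE 0.398 against SD 0.404. At stratum OR 0.4 it gave 3.7% and 4.9%.

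**Power at nominal two-sided 5%.**

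| Arm OR | Stratum OR | Arm only | Arm + strata |
|---|---|---|---|
| 2.0 | 0.25 | 36% | 43% |
| 2.5 | 0.25 | 56% | 64% |

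The repeat set gave 33% and 41% for the first row. For stratum ORs of 0.6 to 0.4 the gain is only about 1 to 3 points. Monte Carlo error on these powers is about √(0.4 × 0.6/3000) = 0.9 points.

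**A second assumed mix** (reference-arm response 55%, severe 67%, ibrutinib 34%; 1,500 trials per setting).
- Stratum OR 0.5: marginal OR 1.94; SE 0.374 against 0.384; power 40.8% against 43.1%.
- Stratum OR 0.33: marginal OR 1.86; SE 0.373 against 0.396; power 39.7% against 43.7%.
- With equal arms, one-factor rejection was 4.7% and 4.5%, adjusted 5.9% and 5.8%, with Monte Carlo error of about 0.6 points. Here the one-factor test is barely conservative.

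**At the difference the documents suggest.** The earlier study had 65% on QD and 63% on BID (SAP 3.1), so OR = (0.65/0.35)/(0.63/0.37) = 1.09. With stratum ORs of 0.25 to 0.4 the marginal OR is 1.075 to 1.083, and power is about 4% with either model.

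**The case against.** The strongest reply is that little depends on this model. It is labelled exploratory, carries no alpha and tests no stated between-arm hypothesis. Both regimens were chosen because they had responded alike, and at an odds ratio near 1.09 neither model would detect anything. The stratum odds ratios and prevalences behind the figures are assumptions. The multivariable step could bring the strata in, and ORR is already repeated within each stratum as a subgroup analysis. All of this stands and limits the point to a minor one. It does not close the gap: the multivariable step commits to nothing, and subgroup ORRs do not give a stratum-adjusted arm effect.

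A reader might also infer three stronger things that the documents and the arithmetic do not support:
- **That the one-factor odds ratio is less precise.** It is not. In logistic regression, adding prognostic covariates increases the standard error of the log odds ratio, here from 0.361 to 0.395. The expectation of a smaller standard error comes from linear models.
- **That it is biased toward 1.** Randomization supports it as an estimate of the marginal odds ratio. The gap between 2.0 and 1.79 is a difference of estimand, it vanishes when the arms are equal, and the SAP does not say which of the two it wants.
- **That efficacy conclusions or the choice of dose are affected.** The primary tests compare each arm with 30% and do not use this model, and the SAP gives it no role in selecting a regimen.

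**Conclusion.** The point holds as a small improvement to an exploratory analysis. The arm model omits both randomization strata, and nothing else in SAP 3.8.5 commits to including them. If the strata are strongly prognostic (assumed odds ratio 0.25 each), the test runs at about 3% instead of 5% and gives up about 7 points of power at an arm odds ratio of 2.0. At an assumed 0.6 the loss is about 1 point, and in the second mix, with 0.5 and 0.33, the conservatism is hard to tell from simulation error. What adjustment buys is a standard error that matches the design, modestly higher power if the arms differ, and a covariate set fixed in advance. A narrower interval on the log odds scale is not among the gains. The primary per-arm results are unaffected.

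**What to change.** In SAP 3.8.5, state that the arm effect is estimated from response ~ arm + prior ibrutinib (yes/no) + severe cGVHD (yes/no), among randomized participants, using the stratum values recorded at randomization, and is reported as a stratum-conditional odds ratio with its interval and p-value. Specifying the values as randomized matters because SAP 3.8.4 refers to severity at screening while the subgroup list in SAP Appendix A refers to baseline. Keep the one-factor models for the other prognostic factors.

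The cost is one line in the SAP and two covariates that were already collected in order to randomize. Sample size, alpha and the primary analysis do not change.

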### **3.9 Concomitant Medications**

Concomitant medications will be coded using WHO Drug Dictionary Enhanced. Concomitant medications are all medications taken after the start of study consent, during the treatment period (day 1 until 28 days after last dose), including those started before but ongoing at the start of study treatment.

Concomitant medications will be summarized according to ATC class and preferred drug name.

### **3.10 Treatment Compliance and Exposure**

The extent of KD025 exposure will be assessed using the duration of KD025 treatment. Pill dispensation and return counts will be the primary source of data.

Duration of KD025 treatment is defined as last dose date – first dose date + 1 day regardless of unplanned intermittent discontinuations. Duration of treatment will be summarized as a continuous variable and also categorically by numbers and percentages for each of the following categories and cumulatively according to these categories: 0 to 6, 6 to 12, and  $\geq 12$  months.

The cumulative duration of treatment will be provided, defined as the sum of the duration of treatment for all patients, and will be expressed in patient years.

The relative dose intensity (RDI) will be presented. The RDI is defined as:

$$\text{RDI (\%)} = 100 * \text{ADI (mg/day)} / \text{PDI (mg/day)}$$

where ADI and PDI are the actual dose intensity and planned dose intensity, respectively:

PDI (mg/day) = planned cumulative dose (mg) / duration of treatment (days),

ADI (mg/day) = actual cumulative dose (mg) / duration of treatment (days).

The planned cumulative dose is the planned daily dose amount \* duration of treatment, while the actual cumulative dose is the sum of actual doses received over the duration of treatment. The actual total dose will incorporate information of dose reductions and dose interruptions captured in the CRF.

Descriptive summary statistics of the treatment duration, actual cumulative dose, ADI, RDI, dose reduction and dose interruption will be presented.

### **3.11 Safety Analysis**

Safety assessments include AEs, serious adverse events (SAEs), vital sign measurements, clinical laboratory evaluations (hematology, chemistry) and ECGs. Clinically significant PE findings will be captured as AEs.

Safety analyses will further include assessments of the defined stopping rules (protocol section 10), namely rates of:

1. Secondary graft failure
2. Histological recurrence of underlying malignancy within 6 months of randomization
3. Withdrawal due to related AEs within 3 months of randomization

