10 STUDY STOPPING RULES

In the event of any of the following safety findings occurring in either treatment arm, after at least 10 participants have been enrolled into the mITT population ([Section 11.2.1](#)) in that arm, enrollment will be paused for assessment of safety:

1. Secondary graft failure in >10% of participants.
2. Histological recurrence of underlying malignancy within 6 months of randomization in >20% of participants.
3. Withdrawal due to related AEs in >20% of participants.

Note: The rates of these events observed in the ongoing KD025-208 study as of 7-Mar-2018, with 51 participants enrolled, were 0%, 4% and 4% respectively.

These stopping criteria will be assessed on an on-going basis by the Medical Monitor and shared with the study Steering Committee ([Section 3.2](#)).

The Sponsor has the right to terminate or to stop the study at any time ([Section 16](#)).

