 - Addition: safety is a secondary endpoint. The primary safety outcome will be the percent of subjects in each arm experience AEs.
 - Addition: Respiratory rate and temperature are vitals that will be measured.
 - Addition: tests to include HBsAg and hepatitis C antibodies
 - Addition: If pregnancy is confirmed with serum testing, KD025 will be discontinued. The sponsor will continue to collect data on the pregnancy and the subject will continue to be followed. In the event that a subject or a subject's partner becomes pregnant during the study, the sponsor will collect data on the pregnancy.
- PHARMACOKINETICS:
 - Addition: new Section 7.1, Sparse PK, describes sparse PK
 - Addition: new Section 7.2, Full PK. Added clarification that samples are collected from subjects that have consented to the optional Full PK sampling and will be performed at sites that have the capability and agree to conduct Full PK sampling.
 - Addition: Sparse PK: additional samples taken at 5 hours post-dose on C2D1 and C4D1 (Table 13)
 - Addition: Full PK: additional samples taken at 5 and 7 hours post-dose on C1D1 and C2D1 (Table 13)
- PHARMACODYNAMICS:
 - Clarification: samples collected from all subjects for PD analyses at only those sites with appropriate capabilities instead of not specifying sites where PD samples collected (8)
- STUDY STOPPING RULES
 - Substitution: that study arm will be terminated early was replaced with enrollment will be paused for assessment of safety (10)
 - Substitution: Withdrawal due to related AEs within 3 months of randomizing in > 20% of subjects was replaced with withdrawal due to related AEs in > 20% of subjects (10)
- STATISTICAL CONSIDERATIONS
 - Substitution: Figure 2 was revised
 - Substitution: Table 11 was revised
 - Addition: three analyses are planned; alpha will only be allocated to the primary endpoint, ORR
 - Interim analysis will be conducted approximately 2 months after 126 subjects have been enrolled in the mITT population.
 - Primary analysis will be conducted approximately 6 months after 126 subjects have been enrolled in the mITT population.
 - Follow-up analysis will be conducted approximately 12 months after 126 subjects have been enrolled in the mITT population.
 - Sample Size (11.2)
 - Addition: Power Calculation added to Section 11.2 header of Sample Size

- Addition: explanation that the Hochberg procedure will be used for multiplicity adjustment for the overall response rate (ORR), the primary efficacy endpoint

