**SIGNATURE PAGE**

## DOCUMENT HISTORY

Version	Author	Description
1.0	██████████	Original Document
2.0	██████████	
Revision according to “KD025-213_Protocol Amendment 1_26Jun19_FINAL”
 
The primary reasons for this new version include:
 

• Change of study design: add a formal interim analysis with alpha spending .0025

• Change definitions of duration of response in accordance with FDA type B meeting held on 01 May 2019

• Rearrange and add some secondary efficacy endpoints

• Add subgroup analysis for proton pump inhibitor

2.1	██████████	
The primary reasons for this new version include:
 

• Add censoring rule of new systemic cGVHD treatment for organ and overall response, corticosteroids usage and Lee symptom score

• Change term of “Sponsor Assessments” into “Kadmon Algorithmic Response Assessments (KARA)”

• Add some additional analyses (section 3.8.2.12)

• Add analyses of PROMIS for responder and nonresponder populations

• In subgroup analyses: add baseline GFR, change age into <65 / ≥65 from by 50 percentile

• Clarify response assessment in appendix B

• Minor typo and wording changes

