**Table 5: Safety TLFs**

T/F/L	Title	Population
-------	-------	------------

T	Concomitant medications	miITT
L	Concomitant medications	miITT
T	Treatment exposure and compliance	miITT
L	Treatment exposure and compliance	miITT
T	Dose modifications and interruption	miITT
L	Dose modifications and interruption	miITT
T	Overall summary of TEAEs	Safety
T	TEAEs by Soc/PT	Safety
T	TEAEs by PT	Safety
T	TEAEs by severity and PT	Safety
T	Treatment related AEs by PT	Safety
T	Serious TEAEs by Soc/PT	Safety
T	Serious TEAEs by PT	Safety
T	Treatment related SAEs by PT	Safety
T	Grade 3-5 TEAEs by Soc/PT	Safety
T	Grade 3-5 TEAEs by PT	Safety
T	Treatment related grade 3-5 AEs by Soc/PT	Safety
T	TEAEs leading to Study treatment discontinuation by Preferred Term	Safety
T	Related TEAEs leading to Study treatment discontinuation by Preferred Term	Safety
T	TEAEs leading to dose interruption by Preferred Term	Safety
T	Related TEAEs leading to dose interruption by Preferred Term	Safety
T	TEAEs leading to dose modification by Preferred Term	Safety
T	Related TEAEs leading to dose modification by Preferred Term	Safety
T	TEAEs leading to dose reduction by Preferred Term	Safety
T	Related TEAEs leading to dose reduction by Preferred Term	Safety
L	AEs	Safety
L	AE Leading to treatment discontinuation	Safety
L	Death	Safety
T	Lab values and their change from baseline	Safety
F	Lab values by visit	Safety
T	Shifts in CTC grade from baseline to highest grade post-baseline of laboratory	Safety
L	Lab values with CTC grade $\geq 3$	Safety
T	Vital signs and their change from baseline	Safety
L	Vital signs	Safety
T	ECG parameters and their change from baseline	Safety

F	ECG parameters by visit	Safety
T	Number and percentage of subjects with QTcF by visit a) absolute ranges and b) change from baseline	Safety
T	QTcF abnormalities	Safety
L	ECG values	Safety

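### SAP 3.11 reports related-AE withdrawals only within 3 months of randomization, although the protocol Section 10 stopping rule it cites has no time window

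*SAP*

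**What the plan says.** SAP 3.11 introduces three rates with the words "Safety analyses will further include assessments of the defined stopping rules (protocol section 10), namely rates of". The third is "Withdrawal due to related AEs within 3 months of randomization".

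Protocol Section 10 lists three safety findings that pause enrollment if they occur in either arm once at least 10 participants are in that arm's mITT population. The third is "Withdrawal due to related AEs in >20% of participants". The second, recurrence of the underlying malignancy, carries a 6-month window, and the SAP repeats that window correctly. The first, secondary graft failure, has no window in either document.

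The amendment history in protocol Section 21.15.1 records the change: "Withdrawal due to related AEs within 3 months of randomizing in > 20% of subjects was replaced with withdrawal due to related AEs" with no time limit. The SAP Document History says version 2.0 was revised according to "KD025-213_Protocol Amendment 1_26Jun19_FINAL". Version 2.1 followed, and its list of main changes does not mention the stopping rules.

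**The concern.** The SAP names its source and then defines a different quantity. Both texts are current, so the conflict does not depend on the amendment log, which only shows where the 3-month limit probably came from.

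A reader of the clinical study report would take the item 3 rate as the Section 10 result. A withdrawal for a related AE in month 4 or later counts under Section 10 but not under the SAP. For a safety rate, this is the wrong direction in which to err. Treatment continues until clinically significant progression, so related-AE withdrawals after month 3 are possible.

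**Working it through.** **Comparison of the two lists**

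| Item | Protocol Section 10 | SAP 3.11 | Match |
|---|---|---|---|
| 1. Secondary graft failure | no window, >10% | no window | yes |
| 2. Recurrence of malignancy | 6 months, >20% | 6 months | yes |
| 3. Withdrawal for related AEs | no window, >20% | 3 months | **no** |

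The match column refers to event and window; SAP 3.11 states no thresholds. Section 10 gives a window where one is meant, so its absence from rule 3 should be read as intended.

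**Direction.** SAP 3.14 makes the denominator the number of subjects in the analysis population or group, unless otherwise specified. Write N for that number in an arm, W for all related-AE withdrawals and W3 for those within 3 months of randomization. Since W3 ≤ W, W3/N ≤ W/N. The two rates are equal only if no such withdrawal occurs after month 3.

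**Size at the limit.** Take N = 63 per arm (SAP 3.1 and 3.2).
- 12/63 = 19.0%, not above 20%.
- 13/63 = 20.6%, above 20%.
- With W = 13, one late withdrawal gives a SAP rate of 12/63 = 19.0%; three give 10/63 = 15.9%; six give 7/63 = 11.1%. These splits are assumptions, because the documents do not say when such withdrawals occur.

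**Follow-up outside the window.** The primary and follow-up analyses come about 6 and 12 months after 126 subjects are enrolled (SAP Section 3). A participant still followed then has at least about that much follow-up.
- At 6 months: (6 − 3)/6 = at least 50% of follow-up time lies outside the window.
- At 12 months: (12 − 3)/12 = at least 75%.

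These are shares of time, not of events. As an illustration only, assume a constant hazard and a 24% cumulative rate W/N at time T months. Then W3/N = 1 − (1 − 0.24)^(3/T).
- T = 6: 12.8%, or 53% of the events.
- T = 12: 6.6%, or 28% of the events.

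**Likelihood of reaching the limit.** Section 10 gives the KD025-208 rates for the three rules: "with 51 participants enrolled, were 0%, 4% and 4% respectively". The third, 4%, corresponds to 2/51 = 3.9%. Applied here, 0.04 × 63 = 2.5 withdrawals are expected per arm. The exact binomial probability of 13 or more of 63 is:

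| True rate | P(13 or more of 63) |
|---|---|
| 4% (KD025-208) | about 1.1 × 10⁻⁶ |
| 8% (assumed) | 0.13% |
| 10% (assumed) | 0.9% |

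The higher rates are included because the KD025-208 figure is dated before the original protocol, which used the 3-month rule. The 4% may itself be a windowed rate; the documents do not say.

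**The case against.** The strongest reply is that nothing is decided on this rate. Section 10 says "These stopping criteria will be assessed on an on-going basis by the Medical Monitor", under the protocol wording, and its consequence is a pause in enrollment. The SAP analyses come only after 126 subjects are in the mITT population, which is the SAP's full planned enrollment. SAP 3.11 lists rates without a threshold or verdict, so the 12-versus-13 example describes a comparison the SAP does not formally plan. This stands, and it limits the consequence to what is reported.

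Second, late events appear elsewhere. SAP 3.11.1 repeats the summaries of TEAEs leading to discontinuation for related events, by arm and without a window. SAP Appendix A plans "Related TEAEs leading to Study treatment discontinuation by Preferred Term", an overall TEAE summary, and a listing of AEs leading to treatment discontinuation. Protocol 11.9 also asks for AEs leading to withdrawal or treatment discontinuation to be summarized overall and by arm. A reader could therefore largely rebuild the count. But none of these outputs is specified as the participant-level rate of related-AE withdrawal for Section 10. The only output given that label uses the wrong definition.

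Third, the timing of withdrawals is unknown. If they come early, the two rates nearly coincide. That is true, and it is why only the direction, not the size, of the error is certain.

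Fourth, the main analyses may already be done, since the current protocol says FDA approval was based on data from this study. If so, the fix has less practical value, although protocol Section 11 still plans additional analyses to include the adolescent and Companion Study participants.

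**Conclusion.** The concern holds. SAP 3.11 item 3 does not report the Section 10 rule it cites, and its rate can only equal or fall below the rate under that rule. The direction rests on the SAP's common denominator and on reading the missing window in Section 10 as deliberate, which the amendment history supports.

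The practical effect is contained. Neither the live pause rule nor the primary endpoint is affected. A different reading against 20% is very unlikely at the 4% rate and stays below 1% even at an assumed 10%. At any underlying rate, though, the reported figure is too low as soon as one related-AE withdrawal occurs after month 3. This should be corrected, but it does not threaten the study's conclusions.

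**What to change.** Delete the 3-month limit from item 3 of the list in SAP 3.11. Report, by arm, the number and percentage of participants withdrawn for related AEs at any time, next to the 20% limit in Section 10. State whether withdrawal there means from treatment or from study, since neither document defines it for this rule. A 3-month rate can stay as a labelled supplementary line.

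The cost is one phrase in the SAP and one summary line. Reasons for withdrawal and AE causality are already collected, so no new data are needed.
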